**Background and Significance:**

For young women who are sexually active with symptomatic pelvic organ prolapse, reconstruction with a sacrocolpopexy procedure is beneficial because the success rates are high as the procedure adequately restores support of the vaginal apex and maintains vaginal length (Walters). Minimally invasive abdominal sacrocolpopexy has become an alternative to open abdominal sacrocolpopexy as this mode of surgery bridges the gap between the advantages of vaginal surgery, namely decreased morbidity and faster patient recovery, with the surgical success rates of abdominal sacrocolpopexy (Ganatra).

Sacrocolpopexy involves suspension of the vagina to the anterior longitudinal ligament of the sacrum at the level of S1 using a bridging graft which can be made of biologic or synthetic materials. The graft is sutured to the anterior as well as the posterior vagina and then attached to the anterior longitudinal ligament of the sacrum. The surgery can be performed for uterovaginal prolapse or post-hysterectomy vaginal vault prolapse. In cases of uterovaginal prolapse, hysterectomy is often performed unless uterine preserving surgery is desired and a hysteropexy is performed. When concurrent hysterectomy is done, a supracervical or total approach may be taken.

In 2014, there was a de facto change in practice patterns after the Food and Drug Administration advised against power morcellation for extraction of the uterine specimen after minimally invasive supracervical hysterectomy. At that time, surgeons performing prolapse surgery had to choose to continue performing concurrent supracervical hysterectomy at the time of sacrocolpopexy using an extended abdominal incision to remove the uterus. An alternative solution became to perform total vaginal hysterectomy followed by a combination of mesh attachment vaginally (to the vagina) and laparoscopically (to the sacrum) versus mesh attachment performed laparoscopically only

(to the vagina and sacrum). Very few studies have looked at the outcomes of these two ways to perform minimally invasive sacrocolpopexy with concurrent hysterectomy. One study published by Nosti et al. did compare the two groups retrospectively and found that there was no difference in mesh-related complications between the groups and that vaginal mesh attachment following vaginal hysterectomy decreased operative time significantly with no differences in intraoperative complications, reoperation for recurrent prolapse, and subjective or objective outcomes compared to concurrent supracervical hysterectomy (Nosti). In our practice, both techniques are currently used, and while we also believe there are no differences in complications and outcomes between the two modes of surgery, anecdotally our group feels that surgical time may be the same between the two types of prolapse repairs.

Cost of health care has become a hot topic in the medical community. One of the focuses of cost containment in medicine has centered around operating room efficiency. Several studies have looked at OR time nonutilization (Weinbaum) in order to determine the economic value of saving OR time. Surgeons can make significant contributions to these types of savings by reducing equipment needs, facilitating case set-up times, and focusing on intraoperative efficiency. This includes choosing a mode of hysterectomy and technique for mesh attachment at the time of sacrocolpopexy that may make the entire procedure faster and more efficient.

Given the sparse data that exist, it remains unclear if one type of concurrent hysterectomy and subsequent mesh attachment at the time of sacrocolpopexy is more efficient. Furthermore, because no prospective studies exist, we also do not know with any degree of certainty if one approach reduces the risk of intraoperative and postoperative mesh-related complications as well as the risk of prolapse recurrence. Therefore, the primary objective of the proposed study is to determine the difference in surgical time between minimally invasive (laparoscopic) sacrocolpopexy performed with concurrent vaginal hysterectomy versus laparoscopic supracervical hysterectomy. The secondary objectives are to determine if there are differences in intraoperative adverse events and postoperative mesh-related complications and prolapse recurrence between the groups.

**Hypothesis:** There is no clinically difference in surgical time in patients undergoing vaginal hysterectomy versus laparoscopic supracervical hysterectomy at the time of sacrocolpopexy

**Study Design:** Randomized trial

**Primary Outcome:** Surgical time defined as time of incision to time of sacrocolpopexy completion (abdominal incisions closed)

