### **Analysis Plan:**

There will be 2 arms to this study: laparoscopic supracervical hysterectomy and sacrocolpopexy with Restorelle® Y mesh and vaginal hysterectomy and sacrocolpopexy using the Restorelle® Dual flat mesh.

We determined that 30 subjects in each arm were needed to detect a difference of 30 minutes or more (standard deviation 30 minutes) in surgical time between the two groups with 80% power and a significance level of .05. We will account for potential subject drop out and loss to follow-up as well as unforeseen factors in recruiting and will plan to recruit 35 subjects to each arm, for a total of 70 subjects.

All statistical analyses will be done using jmp 14. We will use descriptive statistics to show our demographic and baseline data: categorical variables will be presented as n/N (%) with 95% confidence intervals and continuous variables will be presented as mean+/- SD [range]. The two types of hysterectomy (laparoscopic supracervical and vaginal) will be compared. With a continuous outcome and two categorical independent factors, a two-way analysis of variance will be used to evaluate differences between the groups. The results will be presented in a standard ANOVA table, which should be sufficient to determine if differences exist. A linear regression will be done to demonstrate actual changes in surgical time attributed to each variable.

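### The hypothesis claims no clinical difference in surgical time, but the planned ANOVA tests only for a difference from zero, and no margin or between-arm confidence interval is given

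*Combined protocol and SAP*

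**What the plan says.** - **Hypothesis section:** "There is no clinically difference in surgical time in patients undergoing vaginal hysterectomy versus laparoscopic supracervical hysterectomy at the time of sacrocolpopexy". No number of minutes is attached to the word for clinical.
- **Background and Significance:** "the primary objective of the proposed study is to determine the difference in surgical time", with the motivation that "it remains unclear if one type of concurrent hysterectomy and subsequent mesh attachment at the time of sacrocolpopexy is more efficient". The same section records the study group's impression, from its own practice, that the two approaches may take equally long.
- **Analysis Plan, sizing:** 30 per arm to detect a "difference of 30 minutes or more (standard deviation 30 minutes) in surgical time between the two groups with 80% power" at significance level .05, with 35 per arm to be recruited. The 30 minutes is a difference to detect. It is not called a margin and is not linked to the hypothesis.
- **Analysis Plan, comparison:** "a two-way analysis of variance will be used to evaluate differences between the groups". Then: "The results will be presented in a standard ANOVA table, which should be sufficient to determine if differences exist". And: "A linear regression will be done to demonstrate actual changes in surgical time attributed to each variable".
- **Analysis Plan, intervals:** the only confidence intervals mentioned are those for categorical variables, in a sentence introduced as describing demographic and baseline data. Nothing is said about an interval for the difference in surgical time.

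**The concern.** The stated hypothesis and the stated analysis ask different questions. The hypothesis is about a difference large enough to matter clinically. The ANOVA asks whether the difference is zero. With no number of minutes and no interval, the plan gives no way to get from one to the other.

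The text also leaves the type of trial open. The objective and the sizing fit an ordinary trial looking for a difference, and the hypothesis may be its formal null. The word for clinical, together with the group's expectation of similar times, makes an equivalence reading plausible too.

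This concerns the primary outcome. A significant difference of 16 minutes could be reported as contradicting the hypothesis, because p is below .05, or as consistent with it, because it is well under 30 minutes. A non-significant result could be reported as no difference without anyone looking at how large a difference the data still allow. Only a rule fixed in advance prevents a choice made after the result is known.

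**Working it through.** **Inputs from the Analysis Plan:** difference to detect 30 minutes, SD 30 minutes, alpha .05, power 80%, 30 per arm (35 recruited). **Assumptions:** two-sided two-sample t-test with equal arms. The plan does not state sidedness, and its second ANOVA factor could change the residual SD.

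**1. The plan's own figure.** n per arm = 2 × (1.960 + 0.842)² × (30/30)² = 15.7, so 16; the t-test version gives 16.7, so 17. The stated 30 per arm is not reproduced: with those inputs it has about 97% power. Thirty per arm with 80% power for 30 minutes corresponds to an SD of about 41 minutes (40.8). Both SDs are therefore carried forward.

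**2. Smallest significant observed difference.** t(0.975, 2n−2) × SD × √(2/n).
- n = 30, SD 30: 2.002 × 30 × √(2/30) = 2.002 × 7.746 = 15.5 minutes.
- n = 35, SD 30: 1.995 × 7.171 = 14.3 minutes.

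Both are about half of 30 minutes.

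**3. Chance of a non-significant test (noncentral t, SD 30).**

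| True difference | 30 per arm | 35 per arm |
|---|---|---|
| 0 min | 95% | 95% |
| 10 min | 75% | 72% |
| 15 min | 52% | 46% |
| 20 min | 28% | 21% |

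**4. What a non-significant result would show if 30 minutes were the margin.** This margin is an assumption. With 30 per arm and SD 30, the 90% CI half-width is 1.672 × 7.746 = 12.9 minutes. The largest non-significant difference plus this half-width is 15.5 + 12.9 = 28.4, just inside 30. With SD 41, the standard error is 41 × √(2/30) = 10.59; the same sum is 2.002 × 10.59 + 1.672 × 10.59 = 21.2 + 17.7 = 38.9, outside 30. Integrating over the sampling distribution of the SD gives the share of non-significant trials (30 per arm) whose 90% CI lies inside ±30:

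| True difference | SD 30 | SD 41 |
|---|---|---|
| 0 min | 99.5% | 79% |
| 15 min | 96% | 56% |

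At SD 30 and a true difference of 20 minutes it is 93%.

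**5. Chance of showing equivalence** (true difference 0, 90% CI wholly inside the margin, 30 per arm). Margin 30: 97% at SD 30, 75% at SD 41. Margin 20 (also an assumption): 64% at SD 30; 40 per arm would be needed for 80%, above the 35 to be recruited.

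**The case against.** The strongest reply is that this is an ordinary difference trial and the Hypothesis section is simply its null. The objective and the sizing support that reading. On it, a significant ANOVA does contradict the hypothesis, so a reader who infers that no result bears on it at all goes too far. What stands is that such a result contradicts zero difference, not absence of a clinical difference, and that a non-significant result still does not establish the null.

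A second reply is that, at the plan's own SD of 30, non-significance would be quite informative. If 30 minutes were the margin, a non-significant result would nearly always come with a 90% CI inside it. So it would be too absolute to say that the p-value can say nothing about the hypothesis. But this depends on a margin the plan does not adopt and on an SD that does not fit its own sample size. At SD 41 the reassurance largely goes.

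Three stronger readings are not supported:
- **Surgical time will be reported only as mean, SD and range.** The sentence "categorical variables will be presented as n/N (%) with 95% confidence intervals and continuous variables will be presented as mean+/- SD [range" is introduced as covering demographic and baseline data, so it does not govern the primary outcome. The plan is silent on an interval for the difference; it does not exclude one, and the planned regression can supply it.
- **A non-significant ANOVA will be called equivalence.** The plan does not say so. It only fails to rule it out.
- **The 30 minutes is an equivalence margin.** It is given only as the difference to detect.

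Finally, the percentages illustrate the gap under assumed true differences, margins and SDs. They do not measure an error rate of this trial.

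**Conclusion.** The point holds in a limited form: the planned ANOVA does not answer a hypothesis of no clinical difference, because no clinical difference is defined and no interval for the between-arm difference is specified. Under the t-test assumptions with SD 30 and 30 per arm, significance starts at half the difference the trial is sized to detect, while true differences of 15 and 20 minutes are missed 52% and 28% of the time. How far a non-significant result can be trusted turns on the margin, which the plan does not give, and on the SD, which the plan's figures leave uncertain. The trial remains fully analysable. This should be fixed before the data are analysed, and it does not call the design into question.

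**What to change.** Make the primary result the mean between-arm difference in surgical time with its 95% confidence interval, taken from the planned regression. State that a non-significant ANOVA will not be read as no difference. Then choose one of two routes.

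**Default.** Restate the hypothesis as a plain two-sided null and make no equivalence claim. This serves the stated objective, needs no margin and has no sample-size cost. The price is that the claim of no clinical difference is given up.

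**Only if the sponsor wants to keep that claim.** Pre-specify a margin in minutes with its justification, state which interval applies (90%, matching two one-sided 5% tests, or 95%), and conclude no clinical difference only if that interval lies wholly within the margin. Otherwise report that it was not shown. This route may end inconclusive, as the equivalence power at SD 41 or with a 20-minute margin shows, so the SD behind the sample size should be settled first.

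Neither route requires new data items.

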**Secondary Outcomes:**

1. Intraoperative, peri-operative and post-operative complications up to 6 weeks after surgery

2. Pelvic floor symptoms (urinary, bowel, prolapse, sexual function): PFDI, ISI, PISQ) at 6, 12, and 24 months
3. Patient satisfaction (PGII) at 6, 12 and 24 months
4. Prolapse recurrence at 12 and 24 months
5. Mesh-related complication defined by mesh erosion on vaginal examination or report of reoperation for any type of sacrocolpopexy mesh excision within 24 months of the index surgery

**Study Population:** Study subjects will be recruited from patients that present to the Center for Urogynecology & Pelvic Reconstructive Surgery in the Department of Obstetrics and Gynecology at the Cleveland Clinic Main campus, Hillcrest Hospital and Fairview Hospital, and their surgeries will be performed at either one of these sites.

**Inclusion Criteria:**

- Age  $\geq$  18, who are to undergo laparoscopic sacrocolpopexy for uterovaginal prolapse and desire concurrent hysterectomy at the time of surgery
- Other concomitant laparoscopic or prolapse and anti-incontinence procedures (cystocele repair, rectocele repair or mid-urethral sling procedures) will be performed at the primary surgeon's discretion.
- Patient's must have an up-to-date PAP smear on record, or a PAP smear is performed in the office and verified to be normal pre-enrollment

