#### Surgical Interventions

The laparoscopic portions of the surgery will be performed using four ports: an umbilical port for the laparoscope (either 5 or 10/12mm), two ports (either 5, 8 or 10/12 mm) in the bilateral lower quadrants, and one 5-mm port placed at the level of the umbilicus, lateral to the rectus muscle on either side for retraction.

If a supracervical hysterectomy is to be performed, it will be done in a standard fashion. A uterine manipulator will be placed inside of the uterus. The round ligaments will be transected using cautery. The fallopian tubes and ovaries will be left in situ or removed at the time of hysterectomy depending upon the preoperative decision made between the surgeon and patient. The uterine arteries and cardinal ligaments will be cauterized laparoscopically. The uterus will be amputated at the level of the internal cervical os and the endocervical canal will be cauterized. The specimen will be extracted in a laparoscopic endocatch bag and removed through an extended incision at the umbilicus at the end of the case. Dissection of the vagina anteriorly and posteriorly will be done laparoscopically with the use of an end-to-end anastomosis (EEA) sizer in the vagina. Dissection of the presacral space will also be done laparoscopically. Five to six 2-0 PDS sutures will be placed to secure the mesh to the anterior vagina as well as the posterior vagina for a total of 10-12 sutures on the vagina; the arm of the mesh will be secured to the anterior longitudinal ligament of the sacrum using two 0 Prolene sutures. The Coloplast® Restorelle Y mesh will be used for all cases. The peritoneum will be closed with 0 or 2-0 vicryl sutures.

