If a vaginal hysterectomy is performed, it will be done in a standard fashion using a traditional clamp and suture technique starting at the uterosacral ligaments and ending with the utero-ovarian ligaments. The specimen will be extracted through the vagina. Dissection of the vagina anteriorly and posteriorly will be done vaginally. The mesh will be attached vaginally using five to six 2-0 PDS sutures on the anterior and posterior vagina for a total of 10-12 sutures on the vagina. The Coloplast® Restorelle Dual flat mesh will be used. The vagina will then be closed in two layers using 0 or 2-0 vicryl suture. Laparoscopic entrance will then be gained and set up will be done as described above. The presacral space will be dissected laparoscopically and the mesh attached to the anterior longitudinal ligament of the sacrum using two 0 Prolene sutures. The peritoneum will be closed with 0 or 2-0 vicryl sutures.

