### **Data Collection & Management:**

Preoperative data will include the following:

- Patient age, race, vaginal parity, menopausal state, BMI, comorbid conditions, tobacco use, preoperative prolapse stage, preoperative use of vaginal estrogen
- PFDI-20, ISI, PISQ-12

Data points recorded during the procedure will include:

- Total OR time = operating room time of entry and exit
- Surgical time = time from incision to end of sacrocolpopexy (abdominal incisions closed)
- Total Case time = time from incision to end of procedure
- Hysterectomy time = time from start of hysterectomy to end of hysterectomy
- Concomitant procedures
  - Lysis of Adhesions >45 min
  - Anterior colporrhaphy
  - Posterior colporrhaphy
  - Perineorrhaphy
  - Midurethral sling
  - Other
- Estimated blood loss
- Intraoperative complications
  - Vascular Injury
  - Cystotomy
  - Ureteral Injury
  - Bowel Injury - small bowel, large bowel, rectal

Postoperative data will include the following: 6, 12, 24 months

- POP-Q exam (performed by a provider who did not perform the surgery)
- Vaginal exam, inspection for mesh exposure
- PFDI-20, ISI, PISQ-12
- Assessment of use of postoperative vaginal estrogen

- Review of electronic medical record (inpatient notes, d/c summary, ER visits), assessing for postoperative complications
  - Reoperation for immediate complications = reoperation within 30 days of surgery
  - Abdominal Wound infection = fascial, subcutaneous, cutaneous infection requiring antibiotic treatment
  - Hematoma = intrapelvic/abdominal
  - Vaginal cuff cellulitis/Pelvic Abscess = requiring IV/PO antibiotic therapy and/or transvaginal, transgluteal or percutaneous drainage
  - DVT/PE = diagnosed with Doppler US or CT scan
  - Reoperation for SUI with pubovaginal sling (synthetic or fascial), colposuspension, injection with periurethral bulking agents
  - Reoperation for mesh exposure
  - Reoperation for recurrent POP
  - Bowel Injury/Bowel Obstruction = enterotomy, perforation, ileus, partial/complete obstruction
  - Port site or incisional hernia
  - Need for any radiologic imaging
  - Lower urinary tract injury = bladder, ureteral
  - Neurologic Injury = brachial plexus, abdominal wall (ilioinguinal, iliohypogastric), lower extremity (femoral, sciatic, common peroneal)
  - Pulmonary complications = pneumonia, pulmonary hypertension, pulmonary edema within 14 days of surgery
  - Cardiac = ACS, MI, HF within 14 days of surgery
  - Postoperative ICU admission

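### The surgical-time clock stops at abdominal closure but the order of vaginal repairs and slings is not set, so the same repair could count in the vaginal arm and not in the supracervical arm

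*Combined protocol and SAP*

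**What the plan says.** The Primary Outcome entry reads "Surgical time defined as time of incision to time of sacrocolpopexy completion (abdominal incisions closed"), and the intraoperative list under Data Collection & Management gives the same end point. That list also has a longer clock: "Total Case time = time from incision to end of procedure".

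The second bullet of the Inclusion Criteria says that other laparoscopic, prolapse and anti-incontinence procedures "will be performed at the primary surgeon's discretion". It does not place them before or after abdominal closure, and neither does any other section.

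Surgical Interventions describes the arms differently. In the vaginal arm, hysterectomy, dissection, mesh attachment and closure of the vagina come first, all by the vaginal route. Then: "Laparoscopic entrance will then be gained and set up will be done as described above". In the supracervical arm the hysterectomy and mesh suturing are laparoscopic, and "Dissection of the vagina anteriorly and posteriorly will be done laparoscopically". The only vaginal steps described there are placement of a uterine manipulator and an EEA sizer.

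The hysterectomy has its own clock: "Hysterectomy time = time from start of hysterectomy to end of hysterectomy". Colporrhaphy, perineorrhaphy and sling are listed by type only.

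The Analysis Plan gives a two-way ANOVA whose second factor is not named, and then: "A linear regression will be done to demonstrate actual changes in surgical time attributed to each variable". The variables are not listed.

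**The concern.** Randomization balances who needs a repair or sling. It does not balance whether the clock is still running when the repair is done. A surgeon already operating vaginally in the vaginal arm has an occasion to do a repair before laparoscopy begins. The supracervical arm, as described, has no matching stage. If surgeons use that occasion, identical work adds minutes to one arm's primary outcome and none to the other's.

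In that event the error lengthens the vaginal arm's recorded time. The Background cites a retrospective comparison in which the vaginal approach was faster, while the trial's hypothesis is no clinically relevant difference. A bias in this direction would shrink a real saving toward the hypothesis, or produce an apparent excess where the true times are equal.

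**Working it through.** **The plan's own figure.** The Analysis Plan says 30 per arm were "needed to detect a difference of 30 minutes or more (standard deviation 30 minutes) in surgical time" with 80% power at 0.05. This does not reproduce. A two-sided comparison needs 16 per arm by the normal approximation (17 by the t-test), and 30 per arm gives about 97% power. That is a separate matter. Only the 30-minute target, the SD of 30 and the 35 recruited per arm are used below.

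**Standard error.** 30 × √(2/35) = 7.17 min.

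**Bias formula.** Bias (vaginal minus supracervical) = r × d × f, where
- r = share of patients with a vaginal repair or sling, equal in both arms by randomization;
- d = minutes per such patient;
- f = difference between arms in the share of those procedures done before abdominal closure.

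The documents give none of the three. Assumed ranges are r 0.3 to 0.6, d 15 to 30 min and f 0 to 1.

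- f = 0: bias 0.
- 0.3 × 15 × 0.5 = 2.25 min.
- 0.5 × 25 × 0.5 = 6.25 min.
- 0.6 × 30 × 1 = 18 min.

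**Effect on the test.** Simulation with 20,000 trials per case, 35 per arm, SD 30, two-sided 0.05, and early repairs in the vaginal arm only:

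| Bias (min) | Rejection, true difference 0 | Power, vaginal arm truly 20 min faster |
|---|---|---|
| 0 | 5.0% | 79% |
| 2.25 | 6.0% | 68% |
| 6.25 | 12.7% | 45% |
| 18 | 64% | 6% |

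At the design target (vaginal arm truly 30 min faster), the 6.25-minute case gives a mean estimate of −23.7 min and power of 88.5%.

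**Would the planned regression remove it?** It depends on the variable used.
- *Repair performed, yes or no.* The arm estimate stays at 2.2, 6.2 and 18.0 min when the truth is 0. Repair rates are the same in both arms; what differs is whether the minutes are counted.
- *Repair done inside the clock, yes or no.* When the true difference is 0, the estimate returns to about 0.1 min with rejection of 4.6% to 5.1%. In the 6.25-minute case with a true 30-minute saving it gives −30.0 min and 97% power.

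**Can the second variable be built from the listed data?** Often. Total case time minus surgical time shows how much work followed closure, so a recorded repair with almost no gap was done inside the clock. The gap is ambiguous when a patient has several procedures split across closure, and it never gives the in-clock minutes themselves.

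**Direct subtraction.** Removing the in-clock minutes brings estimates to within 0.1 min of the truth, with rejection near 5% (true 0) and power near 79% (true 20-minute saving).

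**The case against.** The plan can be read as already placing repairs after closure. A second clock that runs past abdominal closure makes sense only if work is expected there, and the stepwise account of the vaginal stage includes no repair or sling. On that reading f = 0 and nothing is biased. The discretion in the Inclusion Criteria concerns whether a procedure is done, not when. Nor does the protocol bar a sling or repair before closure in the supracervical arm, which would reduce f. The size of any bias rests wholly on assumed inputs, and at the 30-minute target the middle case still has more than the planned 80% power.

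Most of this stands, and it makes the point a conditional risk. What it does not do is supply a rule. Two surgeons could both follow the protocol as written and have the same repair counted differently.

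A reader might go further and infer that the extra minutes will fall on the vaginal arm. The documents do not support that, because it is a conjecture about what surgeons will do. A reader might also infer that the listed data and the regression cannot correct the problem. That is too strong as well: an in-clock indicator can be derived in many cases and would work. The plan simply does not specify one.

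**Conclusion.** The point holds as a conditional weakness in the primary outcome definition. The clock's end point, the unset order and the single-arm vaginal stage are all in the text. Whether any repair will be done early in the vaginal arm is not. The bias is zero if all repairs and slings follow closure in both arms. Otherwise it is roughly 2 to 6 minutes under moderate assumptions, or up to about a fifth of the target (6.25/30 = 21%). The 18-minute case needs every repair to be in-clock in one arm and none in the other, and should be read only as an outer bound.

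This goes beyond missing detail because exact in-clock minutes cannot be recovered later unless they are timed during surgery. It should be fixed. Confidence is medium, since r, d and f are all assumed.

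**What to change.** 1. In Primary Outcome and in the surgical-time definition under Data Collection & Management, state that vaginal repairs, perineorrhaphy and slings are by default done after the abdominal incisions are closed in both arms, with exceptions at the surgeon's discretion. The choice of procedure stays with the surgeon.
2. For any done earlier, record that it fell inside the clock, with its start and stop times. Report the primary comparison with those minutes excluded.
3. Flag cases where the repair overlaps mesh dissection or another step, since it then has no clean start time.
4. Do not subtract adhesiolysis or adnexal surgery, which are part of the operation being timed.
5. Report the arm difference in total case time beside the primary result. It is already recorded and does not depend on order. It does vary with how many repairs are done, so it is supportive only.

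The cost is a short addition to the outcome definition, a mild default on operative order, and two clock times for each early repair. Subtraction remains imperfect when steps overlap or a second operator works at the same time. No change in sample size is needed for this point.
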